7.1.2 Unscheduled visits

Unscheduled visits may be performed at any time during the study. Depending on the reason for the unscheduled visit (e.g., AE), appropriate assessments will be performed based on the judgment of the investigator. Results of ECGs and laboratory assessments, and changes in concomitant treatment will be recorded in the eCRF. After an unscheduled visit, the regular scheduled study visits must continue according to the planned visit and assessment schedule [Table 1].

Visit	SCREENING PHASE (20–31 days)								TREATMENT PHASE (82–86 days)								FU PHASE (30–37 days)						
	Screening period (7–18 days)				Run-in period (13–24 days)				Double-blind treatment (84 days ± 2 days ¹³)								Run-out period (7 days + 2 days)		FU period (23 days + 7 days) ¹⁷				
	1				2	3			4 ¹⁶	5 (phone call)	6				7	8				9	10	11 (phone call)	
Target Study Days						1 st night	2 nd night			1	7 to 14	1 st night ¹³ 27/28	2 nd night 28/29	55		1 st night ¹³ 83/84	2 nd night 84/85		85/86	92 (+ 2 days)	115 (+ 7 days)		
Evening(PM) / Morning (AM)		PM	AM		PM	AM	PM	AM				PM	AM	PM	AM		PM	AM	PM	AM			
MMSE ¹⁰	X																						
PGA-S ¹¹	X				X	X				←	-----	-----	-----	-----	-----	-----	-----	-----	-----			X	
PGI-C ¹¹ daytime symptoms					X					←	-----	-----	-----	-----	-----	-----	-----	-----	-----			X	
PGI-C ¹¹ night-time symptoms						X				←	-----	-----	-----	-----	-----	-----	-----	-----	-----			X	
PGI-S ¹¹	X				X	X				←	-----	-----	-----	-----	-----	-----	-----	-----	-----			X	
Patient Preferences ¹⁴										X							X						
Contact IRT	X				X					X				X					X				
Randomization ¹²										X													
Dispense IMP wallet(s)					X					X				X					X				
Study drug intake ³					←	-----	-----	-----	-----	-----	-----	-----	-----	-----	-----	-----	-----	-----	-----			→	
SAEs and AEs ⁵	←	-----	-----	-----	-----	-----	-----	-----	-----	-----	-----	-----	-----	-----	-----	-----	-----	-----	-----	-----	-----	-----	→

1. For women of childbearing potential, serum test at V1 and V8 and urine test at V2, V4, V6, V7, V10. 2. The hand-held device is handed out to the subject and completed at home daily from V1 to V10. 3. Daily placebo single-blind treatment during run-in and run-out periods, and daily double-blind study treatment during treatment phase. 4. The 1st PSG can be performed any nights between V1 and V2. It includes assessment of AHI, PLMAI, SpO₂. 5. SAE and AE reporting and follow-up: all SAEs and AEs from signed ICF up to EOS. 6. In the event of permanent study treatment discontinuation, safety assessments of V8 are recommended to be performed within 7 days of last DB study drug intake. If the subject remains in the study, he or she will perform study visits and assessments as planned until EOS (Day 115), without the run-out period (including Visit 9 and Visit 10). 7. Approximately 30 to 60 minutes after PSG lights on. 8. Performed approximately 1 hour after lights on. 9. Height only at V1. 10. For elderly subjects only. 11. PGA-S, PGI-S and PGI-C (daytime symptoms and night-time symptoms questionnaires) will be completed at home once a week between V4 and EODBT. 12. Randomization will take place after all the V4 assessments have been performed and provided the subject fulfills all the eligibility criteria. 13. A time window of ± 2 days is allowed at each visit vs randomization visit (V4). 14. Patient preferences sub-study (PAUSE) available for sites in Germany and in the USA only. 15. In the event of permanent study treatment discontinuation, next day residual assessment of V8 will only be performed if the subjects can be assessed within 24 h of last DB study drug intake. 16. Three working days are required between V3 and V4 to obtain eligibility confirmation regarding objective sleep parameters. 17. If Run-out period exceeded by 2 days, then the follow-up period can only be exceeded by a maximum of 5 days.

AE = adverse event; AHI = apnea/hypopnea index; BWSQ = Benzodiazepine Withdrawal Symptom Questionnaire; C-SSRS[®] = Columbia Suicide Severity Rating Scale; ECG = electrocardiogram; EODBT = End-of-Double-Blind-Treatment; EOS = End-of-Study; ESS[®] = Epworth Sleepiness Scale[®]; FU = Follow-up; ICF = Informed Consent Form; IDSQ = Insomnia Daytime Symptoms and Impacts Questionnaire; IMP = Investigational Medicinal Product; IRT = Interactive Response Technology; ISI[®] = Insomnia Severity Index[®]; MINI[®] = Mini International Neuropsychiatric Interview[®]; MMSE[®] = Mini Mental State Examination[®]; PAUSE = Patient Preferences StUdy in InSomnia; PGA-S = Patient Global Assessment of Disease Severity; PGI-C = Patient Global Impression of Change (daytime symptoms and night-time symptoms); PGI-S = Patient Global Impression of Severity; PK = pharmacokinetic; PLMAI = periodic limb movement with arousal index; PSG = polysomnography; SAE = serious adverse event; SDS[®] = Sheehan Disability Scale[®]; SpO₂ = oxygen saturation by pulse oximetry; V = Visit; VAS = visual analog scale(s).

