5.1.9 Premature discontinuation of study treatment

The decision to prematurely discontinue study treatment may be made by the subject, the investigator, or Idorsia personnel. The main reason for discontinuation must be documented in the eCRF and in the subject's medical charts (e.g., AE, lack of efficacy).

A subject has the right to prematurely discontinue study treatment at any time, without any justification, by withdrawal from study treatment only or by withdrawal from any further participation in the study (i.e., premature withdrawal from the study [see Section 8.2]). Although a subject is not obliged to give his/her reason for prematurely withdrawing from the treatment or the study, it is recommended that the investigator makes a reasonable effort to ascertain the reason(s), while fully respecting the subject's rights.

The investigator must discontinue study treatment for a given subject if, on balance, he/she believes that continued administration would be contrary to the best interests of the subject.

Study-specific criteria for discontinuation of study treatment are described in Section 5.1.10.

A subject who prematurely discontinues study treatment is NOT considered as withdrawn from the study and will be followed up until the planned EOS (Day 115), provided that the subject's consent for this limited participation in the study has not been withdrawn. The subject is recommended to return for safety assessments [see Table 1] within one week of his/her last DB study treatment intake (N.B., next day residual assessments will only be performed if the subjects can be assessed within 24 h of last DB study drug intake). All subjects withdrawn from study treatment are encouraged to follow planned study procedures (e.g., visits, sleep diary and questionnaire completion) until EOS. In this case, the run-out period (including Visit 9 and Visit 10) will not be performed, and subjects will directly enter the follow-up period after Visit 8 (considered as EOT in the event of premature discontinuation). The phone call will be performed as planned 30 days (+ 7 days) later, at Visit 11. This will decrease the amount of missing data which is important from a study integrity perspective. Subjects who prematurely discontinue study treatment or the study for any reason will not be replaced.

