6.5 Safety endpoints

In addition to the standardized collection of AEs, safety data specific to insomnia and its treatment will be assessed as follows:

- Withdrawal effects (physical dependence) upon treatment discontinuation will be assessed based on the changes from last assessment on DB treatment (Visit 8, 2nd morning) to run-out period in the BWSQ total score (Visit 9 and Visit 10), the occurrence of relevant AEs and marked ECG abnormalities.
- Rebound insomnia will be assessed based on objective sleep parameters (WASO, LPS and TST) at Visit 9 as compared to Visit 3. It will also be assessed using subjective sleep parameters (sWASO, sLSO and sTST) from run-out period as compared to baseline.
- Next-day residual effect will be assessed based on changes from baseline (Visit 3) to Month 1 and Month 3 in:
 - Coding sub-test[©]
 - SDS[©]
 - Scores on the VAS (mm)
- SAEs up to 30 days after DB study treatment discontinuation or until enrollment into the extension study.
- TEAEs up to 30 days after DB study treatment discontinuation or until enrollment into the extension study.

- AEs leading to premature discontinuation of the DB study treatment.
- AEs of special interest after adjudication by ISB:
 - narcolepsy-like symptoms (i.e., EDS, cataplexy and complex sleep behavior events including hallucinations/sleep paralysis)
 - suicide/self-injury
- Change from baseline (Visit 3) to Month 1 (Visit 6) and Month 3 (Visit 8) in vital signs (mean of the 2 PSG nights in systolic and diastolic blood pressure [BP] and pulse rate).
- Change from baseline (Visit 1) to Month 3 (Visit 8) in body weight.
- Marked ECG abnormalities on DB study treatment.
- Change from baseline (Visit 3) to Month 3 (Visit 8) and the end of the run-out period (Visit 10) in ECG parameters.
- Marked laboratory abnormalities on DB study treatment.
- Change from baseline (Visit 3) to Month 1 (Visit 6) and Month 3 (Visit 8) in laboratory parameters.
- Occurrence of suicidal ideation and/or behavior on DB study treatment based on C-SSRS[®].

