7 SAFETY VARIABLES AND ANALYSES

7.1 Overview of safety analyses including subgroup analyses

Unless noted otherwise, the SS will be used for tables and listings of safety data.

Safety data described below will be listed.

In the event of permanent study treatment discontinuation, it is recommended to perform the safety assessments of Visit 8 within 7 days of the last DB study treatment intake. Although some subjects may be considered as being off study treatment, the time from the

last DB study treatment intake to the Visit 8 assessments is expected to be short. Therefore, for subjects who prematurely discontinue treatment, the safety data (laboratory tests, ECG, vital signs) measured within 7 days of the last DB study treatment intake will be included as being taken during DB study treatment. A subject who prematurely discontinues treatment may continue the planned study visits until EOS, without the run-out period. Therefore, for subjects who prematurely discontinue treatment, the safety data (laboratory tests, ECG, vital signs) measured more than 7 days from the last DB study treatment intake will be excluded from analyses.

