7.3 Laboratory tests

Laboratory analyses are based on data received from the central laboratory. Laboratory data will be converted into SI units. Unless noted otherwise, summaries and listings will include scheduled, re-test and unscheduled assessments.

Descriptive summary statistics for each scheduled visit (re-test excluded) will be provided for observed values and change from baseline in both hematology and blood chemistry laboratory parameters.

The change from baseline to last value (re-test and unscheduled assessments excluded) in the DB study period for hematology and blood chemistry parameters will be summarized.

Marked laboratory abnormalities are defined in [Table 4](#) below. The number (%) of subjects with marked laboratory abnormalities during DB study treatment will be tabulated. A subject will be counted only once, but may be reported in more than one marked laboratory abnormality criterion of a given parameter. Percentages will be based on the number of subjects at risk, i.e., those having at least one post-baseline value for a given parameter.

Shift from baseline to worst value post-baseline based on laboratory normal ranges will be provided for the following laboratory parameters:

- Liver enzymes: alanine aminotransferase (ALT), aspartate aminotransferase (AST), gamma-glutamyl transferase and total bilirubin (TBIL).
- Thyroid hormones: Thyroid-stimulating hormone, free T₃ and free T₄.
- Lipids: total cholesterol and triglycerides.
- Hematology: leukocytes, neutrophils, lymphocytes, eosinophils.

All laboratory data for subjects with at least one marked laboratory abnormality during DB study treatment will be listed. Any local laboratory data collected will be listed separately.

Table 4 Marked abnormalities in laboratory parameters for reporting

Laboratory parameter	Criteria for marked laboratory abnormalities
Hematology (SI unit)	
Hemoglobin (g/L)	< 100 < 80 > 20 above ULN or > 20 above baseline if baseline > ULN > 40 above ULN or > 40 above baseline if baseline > ULN
Hematocrit (%)	< 32% (Male); < 28% (Female) < 20% > 60% (Male); > 55% (Female) > 65%
Platelets (10 ⁹ /L)	< 75 < 50 > 600 > 999
Leukocytes (10 ⁹ /L)	< 3.0 < 2.0

Laboratory parameter	Criteria for marked laboratory abnormalities
	> 20.0 > 100.0
Neutrophils (10 ⁹ /L)	< 1.5 < 1.0
Eosinophils (10 ⁹ /L)	> 5.0
Eosinophils (%)	> 5%
Lymphocytes (10 ⁹ /L)	< 0.8 < 0.5 > 4.0 > 20.0
Reticulocyte (%)	> 2.5%
Blood chemistry (SI unit)	
ALT (U/L)	> 3 × ULN > 5 × ULN > 10 × ULN

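### Month 3 laboratory and ECG rows can include early stoppers' 'Visit 8' values from much earlier in treatment, some before Month 1, because no day window applies to safety data

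*Protocol*

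**What the plan says.** **Timing of the early visit.** Protocol Table 1, footnote 6: after permanent discontinuation, "safety assessments of V8 are recommended to be performed within 7 days of last DB study drug intake". Protocol 5.1.9 agrees: "The subject is recommended to return for safety assessments" within one week of the last double-blind dose. Subjects are then encouraged to keep to the planned visits, without the run-out. In that setting Visit 8 is "considered as EOT in the event of premature discontinuation".

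**Reporting label.** Protocol 6.5 lists "Change from baseline (Visit 3) to Month 1 (Visit 6) and Month 3 (Visit 8) in laboratory parameters" and, for ECG, "Change from baseline (Visit 3) to Month 3 (Visit 8) and the end of the run-out period (Visit 10) in ECG parameters". Protocol 10.3.3 repeats the Month 3 label for both.

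**Which values are kept.** SAP 7.1 covers laboratory tests, ECG and vital signs of early stoppers. Values "measured within 7 days of the last DB study treatment intake will be included as being taken during DB study treatment"; those "measured more than 7 days from the last DB study treatment intake will be excluded from analyses".

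**How they are summarised.** SAP 7.3: "Descriptive summary statistics for each scheduled visit (re-test excluded) will be provided for observed values and change from baseline" in laboratory parameters. SAP 7.4 uses the same by-visit form for ECG. SAP 7.5 uses scheduled assessments only for vital signs and takes Month 3 as the mean of the two PSG nights at Visit 8.

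**Windows.** SAP 12.8 sets day windows for the subjective diary endpoints. The SAP sets none for laboratory, ECG or vital-sign data.

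**The concern.** A reader takes the Month 3 change-from-baseline row to describe about 84 days of dosing. Under these rules, a subject who takes the last dose on Day 5 and is seen on Day 10 has a record called Visit 8. SAP 7.1 retains it, and nothing in the SAP moves it out of the Visit 8 row. If the same subject also attends near Day 84, that record is discarded as more than 7 days off drug.

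The row then mixes exposure durations. An effect that builds up with dosing would be diluted, and the comparison of Month 1 with Month 3 would be blurred. ECG is the clearest case: Protocol 7.2.3.12 schedules recordings at Visits 1, 3, 8 and 10, so Visit 8 is the only scheduled recording on drug.

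**Working it through.** **Inputs**
- Early stopping: 14 of 356 in the 1-month Phase 2 study (SAP 6.1.4). The documents give no 3-month rate.
- 300 subjects per arm (Protocol 10.5).
- Visit 8 at Day 84 ± 2, so earliest Day 82. Month 1 PSG visit around Day 28 (Table 1).
- Early visit up to 7 days after the last dose, recommended but not required.

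**The plan's own figure.** 14/356 = 3.93%, stated as 3.9%.

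**Timing.** With the last dose on Day *d*, an on-time early visit falls no later than Day *d* + 7.
- Certainly before Day 28 if *d* + 7 ≤ 27, so *d* ≤ 20.
- Certainly before Day 82 if *d* + 7 ≤ 81, so *d* ≤ 74.

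**Size at a constant 3.9% per 28 days** (assumption)
- Daily hazard *h* = −ln(1 − 0.039)/28 = 0.00142.
- Stopped by Day 84: 1 − 0.961³ = 0.112, about 34 of 300.
- Last dose by Day 74: 1 − exp(−74*h*) = 0.100, about 30 of 300.
- Last dose by Day 20: 1 − exp(−20*h*) = 0.028, about 8.4 of 300.

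With attendance *a* at the early visit, the share of the Visit 8 row is *a* × P(last dose by Day 74) / (1 − T + *a*T), where T is the total proportion stopping. Completers are assumed to have a value.

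| T over 84 days | Attendance | Mistimed per arm | Share of row | Certainly before Day 28, per arm |
|---|---|---|---|---|
| 5% | 50% | 6.6 | 2.3% | 1.8 |
| 5% | 100% | 13.3 | 4.4% | 3.6 |
| 11.2% | 50% | 15.0 | 5.3% | 4.2 |
| 11.2% | 100% | 29.9 | 10.0% | 8.4 |
| 15% | 50% | 20.0 | 7.2% | 5.7 |
| 15% | 100% | 40.0 | 13.3% | 11.4 |

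**Effect on a mean.** Suppose stopping days are uniform over Days 1 to 83, the visit follows 0 to 7 days later, and everyone attends. The mean assessment day is 42 + 3.5 = 45.5. If an effect grew linearly to Day 84 and did not wear off after the last dose, the row would understate it by about 0.112 × (1 − 45.5/84) = 5% of that effect.

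**The case against.** The strongest reply is that the mapping is inferred. SAP 7.3 and 7.4 speak of scheduled visits and never use the term Month 3; for these data the label comes from the protocol. Protocol 7.1 requires double-blind visits within ± 2 days of the designated day. Protocol 5.1.9 can be read as describing two events: an extra early contact that borrows the Visit 8 assessment list, and a Visit 8 that stays near Day 84. If the early contact were coded as unscheduled, it would stay out of the by-visit means and still enter the marked-abnormality tables.

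That reading is possible, but no sentence adopts it, and SAP 7.1 itself refers to the early assessments as those of Visit 8. The objection therefore turns *do include* into *can include*; it does not remove the problem.

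Several narrowing points stand in full:
- **Vital signs.** Month 3 is a mean over two PSG nights, which an early safety visit need not supply, and the single-value rule in SAP 10.1 does not name vital signs. Body weight openly uses Visit 8 or the last value on study.
- **Coding sub-test and SDS.** Table 1, footnote 15 limits early testing to within 24 hours of the last dose.
- **ECG.** A reader might infer that the by-visit row is the only on-drug QTc summary. It is not: SAP 7.4 also tabulates marked QTc abnormalities over the double-blind period, including unscheduled recordings.
- **Laboratory data.** SAP 7.3 already has a separate change to last double-blind value.
- **Stopping rate.** Four of the 14 Phase 2 discontinuations were randomised in error or did not meet criteria, which is not a recurring monthly risk. Using 10/356 gives 1 − (1 − 0.0281)³ = 8.2%, about 25 per arm, inside the range above.

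**Conclusion.** The concern holds for the by-visit laboratory and ECG summaries. As written, the rules retain an early stopper's early Visit 8 value, discard a Day 84 value from anyone who stopped more than a week before, and give no window or separate row that keeps the early value out of Month 3.

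The size is modest: about 2% to 13% of the row for 5% to 15% stopping and 50% to 100% attendance. At the Phase 2 monthly rate it is about 15 to 30 values per arm, of which 4 to 8 certainly precede Day 28. These figures depend on a 3-month stopping rate and an attendance rate that the documents do not give.

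A reader might go further and conclude that all Month 3 safety means are contaminated, or that efficacy results are at risk. The documents do not support either. The vital-sign, Coding and SDS definitions limit the exposure, the affected tables are descriptive with no hypothesis tests, and the 7-day rule in SAP 7.1 applies to safety data only. The change is worth making, but it does not threaten the trial's main conclusions.

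**What to change.** In SAP 7.3 and 7.4, and in 7.5 where such values exist, count a Visit 8 record in the Month 3 row only if it falls within the protocol's scheduled Visit 8 window (± 2 days). Show earlier records in a separate row by arm, labelled *premature end of DB treatment*. Keep them in the marked-abnormality, shift-to-worst and last-value tables.

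For that last step, reconcile SAP 7.1 with SAP 12.2. The first treats values up to 7 days after the last dose as on-treatment. The second ends an early stopper's double-blind period at most one day after the last dose, and the marked-ECG and last-laboratory-value tables are defined on that period.

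The cost is SAP wording, one extra row per table and a slightly smaller Month 3 n. No visit, assessment or subject procedure changes.

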7.2 Study assessments

The mandatory study assessments are listed in [Table 1](#).

All study assessments are performed by qualified study personnel (medical, nursing, or specialist technical personnel), and are recorded in the medical history and eCRF unless otherwise specified. Study assessments performed during unscheduled visits will also be recorded in the eCRF.

The following order of assessments is recommended:

- In the evening before a PSG night:
 - Urine drug screen and alcohol test
 - IDSIQ
 - Evening questionnaire in sleep diary (including VAS)
 - PGA-S daytime symptoms (in the first evening at Visits 3, 6 and 8)
 - PGI-C daytime symptoms (in the first evening at Visits 3, 6 and 8)
 - Recording of concomitant medications
 - AEs and SAEs
 - Study drug intake (30 minutes before lights off)
- In the morning after a PSG night (subject fasted):
 - Blood samples (hematology and blood chemistry, only second morning at Visits 3, 6 and 8; PK, only second morning at Visits 6 and 8).
- In the morning after a PSG night and after completion of normal morning routine (e.g., using the bathroom, eating breakfast):
 - Vital signs
 - C-SSRS[©] (only second morning at Visits 3, 6 and 8)
 - Coding sub-test[©]
 - ISI[©] (only second morning at Visits 3, 6 and 8)
 - ESS[©]
 - SDS[©]
 - BWSQ (only second morning at Visits 3, 6, 8 and 9)
 - Morning questionnaire in sleep diary (including VAS)
 - PGI-S night-time symptoms (in the first morning at Visits 3, 6 and 8)
 - PGI-C night-time symptoms (in the first morning at Visits 3, 6 and 8)
 - Recording of concomitant medications
 - AEs and SAEs
 - Neurological examination
 - 12-lead ECG (only second morning at Visits 3 and 8)
 - Patient preferences questionnaire PAUSE (only second morning at Visit 8)

The following assessments will be analyzed by an external provider (results will be transferred to the Idorsia database and to the investigators):

- Laboratory parameters
- ECG parameters
- PSG recordings
- Questionnaires completed using a hand-held device (listed below).

If the Principal Investigator (PI) delegates any study procedure/assessment for a subject, to an external facility, he/she must inform Idorsia to whom these tasks are delegated. The set-up and oversight must be agreed upon with Idorsia. The supervision of any external facilities remains the responsibility of the PI.

Calibration certificates / evidence of equipment maintenance for the below-listed equipment used to perform study assessments must be available prior to the screening of the first subject. Calibration certificates of other equipment must be available as per local requirements:

- Temperature measurement devices for study treatment and sample storage area.
- Polysomnographic device.

Use of hand-held and tablet devices

Subjects will be required to complete the following questionnaires on a hand-held device: Epworth Sleepiness Scale[®] (ESS[®]), ISI[®], SDS[®], BWSQ, IDSIQ, PGA-S daytime symptoms, PGI-C daytime and night-time symptoms, PGI-S night-time symptoms, sleep diary (including VAS).

Subjects will be required to complete the following questionnaires on a tablet at site: Patient preferences questionnaire (PAUSE).

Investigators, delegated physicians, specialist nurses or nurse practitioners trained according to local requirements and local clinical practice will be required to complete the following questionnaires on a tablet at the site: C-SSRS[®], MMSE[®].

Sites will be properly trained on the accurate use of the hand-held and tablet devices by the sponsor or an external CRO and are then expected to train their subjects on how to appropriately complete the questionnaires. Data collected from the hand-held devices will be electronically transferred to Idorsia by the CRO.

For further details refer to the tablet and hand-held devices manual.

